#### Study Day

- Calculated as the number of days from date of first dose of mepolizumab in study 201312: Ref Date = Missing →
  - Study Day = Missing
- Ref Date < Date of first dose of mepolizumab in study 201312→

   Study Day = Ref Date Date of first dose of mepolizumab in study 201312
- Ref Data ≥ Date of first dose of mepolizumab →
- Study Day = Ref Date (Date of first dose of mepolizumab in study 201312) + 1

Critical	Baseline Assessments	
Subject	ts meeting Baseline Definition 1 from Section 5.2:	
1.	Demographic information review and update for 201312	
2.	General medical history review and update in 201312	
3.	Physical examination and update in 201312	
4.	Assessment of Inclusion/Exclusion criteria.	
5.	Urine pregnancy test for females of childbearing potential (Protocol Appendix 2: Acceptable Birth	
Subias	Control)	
	Demographic information review and undate for 201212	
ו. ס	Constal medical history review and update in 201212	
Z. 2	Deneral metrical mistory review and update in 201312	
J. 1	Pulmonary function tests and assessment	
4. 5	Assessment of Inclusion/Evolusion criteria	
5. 6	Liring programmy test for females	
Subject	ts meeting Baseline Definition 4 from Section 5.2	
1	Demographic information review and undate for 201312	
2	General medical history review and update in 201312	
3	Physical examination and update in 201312	
4	Pulmonary function tests and assessment	
5.	Assessment of Inclusion/Exclusion criteria.	
6.	Asthma Control Questionnaire-5 (Protocol Section 6.2.1.2)	
7.	Vital signs (Protocol Section 6.3.10.3)	
8.	12-lead ECG (Protocol Section 6.3.10.4)	
9.	Blood sampling for the following:	
	
 
Clinical chemistry
 
	
	
 
Haematology
 
	
	
 
Liver Analytes
 
	
	
 
Immunogenicity
 
	
10.	Urine pregnancy test for females	
11.5.2	2. Study Population	
Age		

Only year of birth was collected for subjects; actual birth data was not collected.

- GSK standard IDSL algorithms will be used for calculating age where the birth date of all subjects will be imputed as '30th June'.
- Birth date will be presented in listings as 'YYYY'.
- Each subject's derived age will be calculated as an integer value based on their imputed date of birth relative to the date of the subject's Visit 1 date.
  - [(30th June of the year of birth reported on eCRF date of Visit 1)/365.25]

#### Body Mass Index (BMI)

• Calculated as Weight (kg) / Height (m^2)

Percent Predicted FEV1		FEV1	Predicted	Pe
------------------------	--	------	-----------	----

FEV1 % of predicted normal will be derived using the Global Lung Function Initiative 2012 lookup tables which are based on the Quanjer equations [Quanjer, 2012] according to the Race/Ethnicity designations specified below:

Collected Race 	Quanjer Designation
African American/African Heritage	African-American calculation will be applied
American Indian or Alaskan Native	Other calculation will be applied
Asian-Central/South Asian Heritage	South East Asian calculation will be applied
Asian-East Asian Heritage	North East Asian calculation will be applied
Asian-Japanese Heritage	Other calculation will be applied
Asian- Southeast Heritage	South East Asian calculation will be applied
Native Hawaiian or Other Pacific Islander	Other calculation will be applied
White-Arabic/North African Heritage	Caucasian calculation will be applied
White-White/Caucasian/European Heritage	Caucasian calculation will be applied
NOTES:	-

 
If multiple races are selected for a single sub
 
	piect then the "Other" calculation will be applied

#### **FEV1/FVC Ratio**

Pre-bronchodilator FEV1/FVC ratio will be calculated as the ratio of the FEV1 and FVC values.

#### Baseline OCS daily dose

- Only corticosteroids administered via oral, intravenous (IV) and intramuscular (IM) routes are to be considered when calculating a subject's total daily prednisone/prednisolone asthma maintenance dose at baseline. All steroids administered via a sublingual route will also be considered as oral.
- The corticosteroid conversion factors shown below will be used, regardless of the route of administration, to scale each corticosteroid dose to a prednisone equivalent dose. These three routes of administration (oral, IV and IM) are to be considered equivalent as it has been noted that the bioavailability of methylprednisolone is considered to be roughly equivalent following administration as an oral, IV or IM steroid.

Standardised Medication Name	Scaling Factor
Betamethasone	8.33
Betamethasone Dipropionate	8.33
Betamethasone Sodium Phosphate	8.33
Cortisone	0.2
Cortisone Acetate	0.2
Cortivazol	17
Deflazacort	0.833
Dexamethasone	6.67
Dexamethasone Sodium Phosphate	6.67
Fludrocortisone Acetate	0
Hydrocortisone	0.25
Hydrocortisone Sodium Succinate	0.25
Hydrocortisone Sodium Phosphate	0.25
Meprednisone	1

Methylprednisolone	1.25
Methylprednisolone Acetate	1.25
Methylprednisolone Sodium Succinate	1.25
Methylprednisone	1.25
Methylprednisone Acetate	1.25
Methylprednisolone Sodium Succinate	1.25
Methylprednisone	1.25
Methylprednisone Acetate	1.25
Prednisolone	1
Prednisolone Acetate	1
Prednisolone Hemisuccinate	1
Prednisolone Sodium Succinate	1
Prednisone	1
Prednisone Acetate	1
Triamcinolone	1.25
Triamcinolone Acetonide	1.25

### 11.5.3. Efficacy

### Patient Reported Outcomes/Questionnaires

#### ACQ-5

- Each question on the ACQ-5 is scored on a 7-point scale from 0 = no impairment to 6 = maximum impairment. The questions are equally weighted and the ACQ-5 score will be the mean of the 5 questions, thus giving a score between 0 (totally controlled) and 6 (severely uncontrolled) [Juniper, 1999; Juniper, 2005].
- If a subject does not complete 1 of the 5 questions at a visit, then the ACQ-5 score will be the mean of the responses to the remaining 4 questions at that visit.
- If a subject does not complete more than 1 of the 5 questions at a visit, then their ACQ-5 score will be set to missing at that visit.
- A subject will be deemed a responder if the subject has a ≥0.5 reduction in ACQ score from Baseline. ACQ-5 Responder/Non-responder category will be missing if the overall ACQ-5 score is missing.

#### Exacerbations

An exacerbation of asthma as defined as:

Worsening of asthma which requires use of systemic corticosteroids and/or hospitalisation and/or Emergency Department (ED) visits.

- For all subjects, i.v. or oral steroid (e.g., prednisone) for at least 3 days or a single IM CS dose is required. For subjects on maintenance systemic corticosteroids, at least double the existing maintenance dose for at least 3 days is required.
- Within each subject, exacerbations that occurred less than seven days apart will be collapsed into a single exacerbation. Exacerbations for which the collapsing has already been performed

#### Exacerbations

will be included in the summaries and analyses. Exacerbations will be displayed in listings as captured within the eCRF. Exacerbations which are collapsed into a single exacerbation will be highlighted.

- The collapsed exacerbation records will be constructed as follows:
  - Start date (ASTDT) is the start date of the first exacerbation in the series
  - o End date (AENDT) is the end date of the last exacerbation in the series
  - Outcome (CEOUT) is the worst outcome in the series (worst to best is Fatal, Not Resolved, Resolved)
  - Cause (EBCAUSE) is the cause associated with the first exacerbation in the series
  - Withdrawal due to exacerbation (EBWD), OCS taken for exacerbation (OCSEXB), corticosteroids taken for exacerbation (CTSEXB), hospitalization due to exacerbation (HSPEXB), emergency visit due to exacerbation (EREXB), and intubation for exacerbation (INTUBEXB) are set to 'Y' if any value for the respective variable in the series equals 'Y'
  - Number of telephone calls (TPCNUM), home day visits (HMDYVSN), home night visits (HMNTVSN), home day+night visits (HMDYNTV), office visits (OFCVSN), urgent care/outpatient visits (UCOUTVSN), emergency room visits (ERVSN), days in intensive care (ICSDYNUM), days in general ward (GWDYNUM) and days hospitalized (HSPDYNUM) are the sum of all of the values in the series for each respective variable

### 11.5.4. Safety

#### Extent of Exposure

- Number of days of exposure to study drug will be calculated based on the formula: Duration of Exposure in Days = Last mepolizumab dose in study 201312 – (First mepolizumab dose in study 201312) + 29 days
- The extent of exposure will also be summarised as the number of study treatments administered

#### **Adverse Events**

Adverse events will be coded using the Medical Dictionary for Regulatory Activities (MedDRA) coding dictionary. Classification of an AE as pre-, on- or post-treatment will be made with reference to the study treatment start and stop dates and the AE onset date. If the AE onset date is missing or partial then the AE will be considered on-treatment unless there is evidence to the contrary (e.g. the month of the onset date is present and is less than the month of the first dose of study medication). AEs with onset up to 4 weeks after the last dose of treatment will be considered on-treatment. AEs with onset after this period will be considered post-treatment but will be assigned to the treatment previously received.

Any SAEs for screen failures or run-in failures will be classified as pre-treatment SAEs.

The most frequent on-treatment AEs will be defined as AEs with frequency  $\geq$ 3% (prior to rounding).

### Adverse Events of Special Interest

Section 7.3 provides a full list of AEs of special interest for this compound.

Adverse events of special interest (AESIs) of anaphylaxis reactions, systemic reactions, and local injection site reactions are collected via targeted eCRF. Systemic reactions with preferred terms such as injection related reaction or administration related reaction will be considered nonallergic reactions; those with other preferred terms will be considered allergic/hypersensitivity reactions.

The AESIs of opportunistic infections, malignancies, serious CVT events and serious ischemic events will be identified from a list of relevant preferred terms maintained within a project level reference dataset; created based on the latest version of the MedDRA dictionary available at the time of database freeze for this study (See Program Safety Analysis Plan for additional details).

#### Exposure Adjusted Adverse Events

The number of events per 1000 subject-years of exposure will be calculated as:

### 1000 \* Number of Adverse Events

(Total Duration of Exposure in Days)/365.25

### **ECG Parameters**

### **RR** Interval

All ECG parameters required in this study will be databased, and therefore, further derivations will not be performed by Stats and Programming. The definitions of these parameters are given in this section.

- If RR interval (msec) is not databased, then RR can be derived as:
  - [1] If QTcB is machine read & QTcF is not provided, then:

$$RR = \left[ \left( \frac{QT}{QTcB} \right)^2 \right] * 1000$$

[2] If QTcF is machine read and QTcB is not provided, then:

$$RR = \left[ \left( \frac{QT}{QTcF} \right)^3 \right] * 1000$$

• If ECGs are manually read, the RR value should be a collected value and will not be derived.

Corrected QT Intervals

- When not databased, corrected QT intervals by Bazett's (QTcB) and Fredericia's (QTcF) formulas will be calculated, in msec, depending on the availability of other measurements.
- If RR interval (msec) is provided then missing QTcB and/or QTcF will be derived as:

$$QTcB = \frac{QT}{\sqrt{\frac{RR}{1000}}}$$

$$QTcF = \frac{QT}{3\sqrt{\frac{RR}{1000}}}$$

• Individual maximum QTc(F) and QTc(B) values will also be summarised by treatment group for each scheduled study visit to show the number of subjects with maximum values (msec) in the following categories:

• <= 450

#### ECG Parameters

- 450 < to <= 480
- 480 < to <= 500
- > 500
- Additionally, individual maximum changes from baseline in QTc(F) and QTc(B) values will be summarised by treatment group for each scheduled study visit to show the number of subjects with maximum changes (msec) in the following categories:
  - <-60
  - ≥ -60 to < -30
  - ≥ -30 to < 0
  - $\geq$  0 to < 30
  - $\geq$  30 to < 60
  - ≥60

#### **Laboratory Parameters**

- If a laboratory value which is expected to have a numeric value for summary purposes, has a
  non-detectable level reported in the database (values below the lower limit of quantification),
  where the numeric value is missing, but typically a character value starting with '<x' or '>x'
  (or indicated as less than x or greater than x in the comment field) is present, the lower limit
  of quantification for that particular parameter will be used to impute the corresponding
  numeric value as half the lower limit of quantification for that measure (LLQ/2).
- Regarding blood eosinophil laboratory data please reference Section 11.5.5.

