### 7.4. Clinical Laboratory Analyses

Laboratory evaluations including the analyses of Chemistry laboratory tests, Hematology laboratory tests, and liver function tests will be based on GSK Core Data Standards. The details of the planned displays are in Appendix 10: List of Data Displays.

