#### 11.4.2. Reporting Standards

#### General

 The current GSK Integrated Data Standards Library (IDSL) will be applied for reporting, unless otherwise stated

(IDSL Standards Location: https://spope.gsk.com/sites/IDSLLibrary/SitePages/Home.aspx)

- 4.03 to 4.23: General Principles
- 5.01 to 5.08: Principles Related to Data Listings
- 6.01 to 6.11: Principles Related to Summary Tables
- 7.01 to 7.13: Principles Related to Graphics

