### 11.6.2. Handling of Missing Data

Element	Reporting Detail
General	• Missing data occurs when any requested data is not provided, leading to blank fields on the collection instrument:
	
 
These data will be indicated by the use of a "blank" in subject listing displays. Unless all data for a specific visit are missing in which case the data is excluded from the listing.
 

	
 
Answers such as "Not applicable" and "Not evaluable" are not considered to be missing data and should be displayed.
 

	
 
Results which are found to be below the limit of quantification (BLQ) are not missing data and will be included in all displays. See Section 11.5.4 for the handling of this data.
 

	• The ACQ-5 score will be considered as missing if <4 items of the questionnaire are completed at a visit. ACQ-5 Responder/Non-responder category will be missing if the overall ACQ-5 score is missing.
	
 
If a blood eosinophil count of zero is reported, it will be imputed with half of the lowest possible blood eosinophil count, where applicable, prior to log transforming the data (Note: this imputation has typically been 0.5 * 0.01 GI/L = 0.005 GI/L for previous mepolizumab studies).
 

	
 
Missing values will not be imputed for any of the other endpoints.
 

Outliers	• Any subjects excluded from the summaries and/or statistical analyses will be documented along with the reason for exclusion in the clinical study report.

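### The LLQ/2 rule for laboratory values is limited to results below the LLQ but also names '>x' results as triggers, so above-range results are either turned into very low ones or left without an explicit rule

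*SAP*

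**What the plan says.** SAP Section 11.5.4, Laboratory Parameters, sets out the imputation rule in one sentence.

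- **Scope:** a "non-detectable level reported in the database (values below the lower limit of quantification"), for a parameter that should be numeric.
- **Trigger:** records "where the numeric value is missing, but typically a character value starting with '<x' or '>x". The same pair is repeated in words: "or indicated as less than x or greater than x in the comment field".
- **Substitute:** the "numeric value as half the lower limit of quantification for that measure (LLQ/2"). No other value is offered.

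Blood eosinophils are taken out of the rule: "Regarding blood eosinophil laboratory data please reference Section 11.5.5".

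SAP Section 11.6.2 refers back to Section 11.5.4, but only for results at the low end: "Results which are found to be below the limit of quantification (BLQ) are not missing data and will be included in all displays". The same section ends its list with a default that endpoints not already mentioned are not imputed.

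Two passages defer to sponsor standards that are not part of these documents. SAP Section 7.4 says the chemistry, haematology and "liver function tests will be based on GSK Core Data Standards". Section 11.4.2 says: "The current GSK Integrated Data Standards Library (IDSL) will be applied for reporting, unless otherwise stated".

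**The concern.** A result reported only as greater than some limit is an above-range result, and half the LLQ is the wrong end of the scale for it. The sentence therefore cannot be applied as a whole, and the programmer has to decide which part governs.

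Clinical laboratory parameters are a secondary endpoint in both documents, and SAP Section 7 calls long-term safety the main interest of the study. What is at stake is how individual subjects are classified in categorical and extreme-value displays, where averaging does not dilute one wrong value. SAP Section 11.5.1 counts a subject with both High and Low values in both categories of the any-visit post-baseline row. A single reversed value can therefore add a false Low and, if no other visit is High, remove the true High.

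**Working it through.** The plan states no figure of its own here, so there is none to reproduce. The inputs are the flags of potential clinical importance (PCI) in SAP Section 11.7.1 and the planned number of subjects in Protocol Section 4.1. Neither document gives an LLQ, or any upper reporting limit x, so break-even values are shown instead.

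**Reading A: the trigger list governs.** A '>x' result becomes LLQ/2. The Low flag is met when the value is below L, and LLQ/2 < L exactly when LLQ < 2L.

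| Analyte | Low flag L | High flag | Flagged Low if LLQ is below 2L |
|---|---|---|---|
| Hematocrit (ratio) | 0.201 | 0.599 | 0.402 |
| Haemoglobin (g/L) | 71 | 199 | 142 |
| Platelets (x10^9/L) | 31 | 1499 | 62 |
| WBC (x10^9/L) | 1.1 | none | 2.2 |
| Calcium (mmol/L) | 1.50 | 3.24 | 3.00 |
| Glucose (mmol/L) | 2.2 | 27.8 | 4.4 |
| Phosphorus (mmol/L) | 0.32 | none | 0.64 |
| Potassium (mmol/L) | 2.8 | 6.5 | 5.6 |
| Sodium (mmol/L) | 120 | 160 | 240 |

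An assay that can report a number at the Low flag has LLQ ≤ L, which is below 2L, so the condition is met. WBC and phosphorus have no High flag, so for them the PCI error is a false Low only. For the other seven, a High can become a Low.

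Illustration: take a glucose result of '>27.8' mmol/L and assume an LLQ between 0.1 and 2.0. The imputed value is 0.1/2 = 0.05 to 2.0/2 = 1.0, below 2.2 and so flagged Low.

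The liver flag needs ALT above 239 U/L (age 13+) or above 143 U/L (age 3-12), together with total bilirubin above 43.

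- ALT, age 13+: LLQ/2 > 239 needs LLQ > 478 U/L.
- ALT, age 3-12: LLQ/2 > 143 needs LLQ > 286 U/L.
- Bilirubin: LLQ/2 > 43 needs LLQ > 86, in the units of that limit.

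Below those LLQs, a '>x' result fails its part of the flag however high the true value is.

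**Reading B: the scope clause governs.** A '>x' result is outside the rule. Section 11.6.2 returns only below-limit results to Section 11.5.4. Section 11.5.5 deals with zero eosinophil counts. Neither document mentions an upper limit of quantification. The no-imputation default in Section 11.6.2 arguably leaves these results out of numeric summaries. It does not settle the matter, because that section describes missing data as blank fields and the default speaks of endpoints.

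**Displays at risk under reading A, so far as they use the imputed number.**

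- Tables 2.54, 2.55, 2.57 and 2.58: normal-range and PCI categories.
- Tables 2.53 and 2.56: change from baseline.
- Figures 2.1 and 2.2: maximum ALT and bilirubin. In Figure 2.1 a baseline '>x' ALT also moves the point.
- Listing 47: a false Low still brings the subject into the listing, with the wrong direction. A failed ALT or bilirubin flag can leave the subject out.

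**Visit means.** Compared with using x, one such result lowers a mean over n subjects by (x − LLQ/2)/n, which is less than x/n. With n = 375 this is under 1/375 = 0.27% of x. The bound is relative to x, not to the mean, and x may be many times the mean.

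**The case against.** The strongest reply is that the harmful reading is the weaker one. The operative condition is a result below the LLQ, the '<x' or '>x' text only describes how such a record usually looks, and Section 11.6.2 reads the rule the same way. This is the more natural construction, and it largely stands. A reader might infer that the SAP definitely plans to convert high results into low ones; the documents do not support that. But the above-limit trigger appears twice, once as a symbol and once in words, so it is not a stray character, and reading B still leaves '>x' results with no explicit rule.

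A second reply is that the sponsor's standards may already cover these results. They may, and the documents cannot settle it. However, Section 11.4.2 lets the SAP override the library, and Section 11.5.4 can be taken as doing so.

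A third reply concerns consequence. A reader might infer that serious liver cases would be missed. The documents do not support this:

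- The central laboratory sends results to the investigator (Protocol Section 6.3.10.1).
- Abnormalities judged clinically significant are recorded as adverse events unless associated with the underlying disease (Protocol Section 6.3.3).
- The stopping and reporting rules (Protocol Sections 6.3.1 and 6.3.9) do not depend on SAP imputation.
- Listings 41 and 42 report liver events and the related chemistry separately.

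An effect on Table 2.59 or Listing 45 cannot be shown either, because their criteria are in shells that are not visible. These limits stand.

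**Conclusion.** The rule is inconsistent as written, and that conclusion rests on the text alone. Following its trigger list would give a wrong result: above-range values would meet the PCI Low flag at any LLQ below the tabulated limits, and '>x' ALT values would fail the ALT part of the liver flag at any LLQ below 478 or 286 U/L by age group. Under the more natural reading, the defect is a missing rule, unless an unseen sponsor standard supplies one.

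The practical size is unknown. The number of '>x' results is not stated and may be zero. A reader might also infer from the x/n bound that visit means barely move, but the documents give no value of x relative to a mean, so that is not established.

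The study is single-arm and descriptive, and the primary endpoints, liver stopping rules and individual care are unaffected. The severity is minor.

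**What to change.** In SAP Section 11.5.4:

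1. Delete '>x' and the words for it from the LLQ/2 rule, so that the rule applies only to '<x' results.
2. Add a rule for '>x' results. For normal-range and PCI flags, treat the result as exceeding x, so that a glucose of '>27.8' counts as High. Simply setting it to 27.8 would miss the flag, which requires a value strictly above 27.8.
3. In numeric summaries and plots, use x as a lower-bound value and footnote the number of such results. In listings, show the character result as reported.
4. If a sponsor standard already covers '>x' results, cite it here in place of items 2 and 3.

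The cost is about two sentences and a small programming change, with no new data. Protocol Section 8.3 has the analysis plan finalised before database freeze, so the rule should be settled by then. The downside is small: x understates the true value in numeric summaries, and where x lies below a High flag the category stays undetermined. The footnote count makes the number of such results visible.

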### 11.5.5. Pharmacodynamic

#### Laboratory Assessments

#### Blood Eosinophils

Blood eosinophils will be log-transformed prior to analysis. Summary statistics will include geometric mean, and a measure of spread (SD or SE) on the natural log scale. If a blood eosinophil count of zero is reported, it will be imputed with half of the lowest possible blood eosinophil count, where applicable, prior to log transforming the data (Note: this imputation has typically been 0.5 \* 0.01 GI/L = 0.005 GI/L for previous mepolizumab studies).

